SD	Standard Deviation
SHSC	Sunnybrook Health Sciences Centre
SUADR	Serious Unexpected Adverse Drug Reaction
TSAT	Transferrin Saturation
WHO	World Health Organization

PROTOCOL SUMMARY

PRINCIPAL INVESTIGATOR	[name]
PROTOCOL TITLE	Daily vs. every other day oral iron supplementation in patients with absolute iron deficiency anemia (DEODO): a multi-centered, pilot randomized controlled trial
PROTOCOL NUMBER	1534
PHASE	III
INVESTIGATIONAL PRODUCT AND PLANNED USE	To evaluate the effectiveness of oral ferrous sulfate (oral iron), 300mg oral tablets and vitamin C 500mg, once daily versus every other day to improve hemoglobin 12 weeks post-initiation
STUDY DESIGN	A phase III, multi-centered, randomized, pragmatic, open-label, controlled pilot trial
DURATION OF FOLLOW-UP	From first dose of study drug to final study visit = 12 weeks
TREATMENT ALLOCATIONS	Experimental arm: Ferrous sulfate 300mg oral and vitamin C 500mg every other day x 12 weeks Control arm: Ferrous sulfate 300mg oral and vitamin C 500mg every day x 12 weeks
PATIENT POPULATION	Patients with iron deficiency anemia defined as hemoglobin less than 120 g/L in women or less than 130 g/L in men; AND ferritin less than 30 mcg/L
SETTING	A multi-centre study, outpatient clinical setting
PLANNED SAMPLE SIZE	52 patients The anticipated duration for this study's recruitment period is 2 years.
PATIENT INCLUSION/EXCLUSION	
Inclusion criteria:
 
 • Age \geq 16 years; • Outpatients with iron deficiency anemia defined as Hb less than 120 g/L in women or 130g/L in men; AND ferritin less than 30 mcg/L 
Exclusion criteria:
 
 • Pregnancy • Currently breastfeeding • Known history of inflammatory bowel disease • Known history of celiac disease • Known history of thalassemia or thalassemia trait • Known inherited bleeding disorder • Known intolerance or lack of response to oral ferrous gluconate, sulfate or fumarate in the last 12 weeks • Multivitamin and mineral supplements (35 mg or more of elemental iron per day) in the 2 weeks prior to randomization • Allergy to oral iron • Allergy to any of the following medicinal and non-medicinal ingredients in ferrous sulfate: ferrous sulphate, calcium citrate, crospovidone, FD&C Red #40-Aluminum lake, FD&C Yellow #6-Aluminum Lake, magnesium stearate, microcrystalline cellulose, polyethylene glycol, polyvinyl alcohol, purified water, talc titanium dioxide • Allergy to any of the following medicinal and non-medicinal ingredients in vitamin C: Ascorbic acid, Colloidal silicon dioxide,

	
croscarmellose sodium, magnesium stearate, microcrystalline cellulose and stearic acid
 
 • Intravenous iron therapy in the past 12 weeks • On new anticoagulant therapy initiated in the past 6-months (e.g. warfarin, apixaban, dabigatran, edoxaban, rivaroxaban) • Surgery planned in upcoming 12 weeks • Chemotherapy planned in upcoming 12 weeks • Blood donation planned in upcoming 12 weeks • Previously enrolled in the study • Creatinine clearance less than 30 mL/min • Hemoglobin less than 80 g/L with active bleeding (defined as WHO grade 2 bleeding or higher in the past week)
RANDOMIZATION	Computer generated allocation sequence; stratified in two groups: hemoglobin \geq 100 g/L and hemoglobin < 100 g/L
STUDY OUTCOMES	
Primary Feasibility Outcome: Time to enroll 52 patients
 
Secondary Feasibility Outcomes
 
 • Feasibility: proportion consenting to participate; proportion receiving allocated treatment; proportion completing laboratory tests, FACIT-fatigue scale, side effects questionnaire; adherence 
Secondary Clinical Outcomes
 
 • Mean hemoglobin increment at 4 and 12 weeks • Proportion with complete hemoglobin response at 4 and 12 weeks • Change in ferritin, serum iron and TSAT at 12 weeks • Quality of life (FACIT-fatigue scale) at 4, 8 and 12 weeks • Gastrointestinal adverse effects at 4, 8 and 12 weeks • Need for escalation in therapy • Proportion with a drop in hemoglobin of 10 g/L or more at 4 and 12 weeks
STATISTICAL ANALYSIS	
The results of this pilot trial will be used to assess the feasibility and inform the design of the definitive trial. We will present point estimates of feasibility outcomes with 95% confidence intervals.
 
An intention-to-treat analysis will be performed on all patients randomized for the secondary clinical outcomes. A per protocol analysis will be conducted for patients who have taken at least 90% of the prescribed doses.

[figure not shown]

2.0 INTRODUCTION

This study document is the protocol for research involving human participants. This study is to be conducted according to Canadian and international standards, and in compliance with the protocol, International Conference on Harmonisation Good Clinical Practice E6 (ICH-GCP), World Medical Association Declaration of Helsinki: Ethical Principles for Medical Research Involving Human Participants, as well as applicable regulatory and institutional requirements and research policies.

2.1 Background

2.1.1 Prevalence of iron deficiency anemia (IDA)

Iron deficiency anemia is a global health problem and the most common cause of anemia worldwide.¹ There is significant variation based on geographical location and population studies. In North America and Europe, its prevalence ranges from 1-2% in men² to 2-5% in women²⁻⁵ to 9-11% in adolescent females⁶ and 17-31%^{3,7} in pregnant women.

2.1.2 Consequences of IDA

Iron is an important nutrient for the production of red blood cells but also many biologic functions including energy production, DNA synthesis and cell proliferation.⁸ Patients with iron deficiency (ID) and IDA can present with a multitude of symptoms including fatigue, restless legs syndrome⁹ and pica.¹⁰ In addition, ID can also lead to impacts on physical function. Adverse effects include aerobic capacity (reduced VO₂ max), work intolerance and fatigue¹¹; diminished exercise capacity^{12,13}; cognitive impairment specifically in attention, memory, speed and executive planning function¹⁴⁻¹⁶; and higher risk of depression¹⁷. There may be additional negative manifestations of IDA that have not yet been fully recognized. In one study, even after excluding patients with restless legs and accounting for the presence of depression and anxiety, IDA was still associated with worse sleep quality.¹⁸ In another retrospective cohort study of over 300,000 patients, iron deficiency was associated with combined and sensorineural hearing loss in US adults.¹⁹ Thus ID and IDA have significant consequences which may potentially benefit from treatment.

2.1.3 Definition of IDA

The World Health Organization (WHO) defines anemia as a hemoglobin of less than 120 g/L for females and less than 130 g/L for males.²⁰ Although the definition of anemia is well accepted, the definition of ID is less standardized. Based on a systematic review conducted by Guyatt et al to determine the diagnostic value of laboratory tests in the diagnosis of IDA, serum ferritin was found to be the most predictive and a better diagnostic test than mean cell volume (MCV) and transferrin saturation (TSAT).²¹ Serum ferritin values between 15-25 mcg/L were associated with a likelihood ratio (LR) of 8.83 for ID. Goodnough et al found that a serum ferritin of less than 30 mcg/L was associated with a sensitivity of 92% for IDA and a positive predictive value of 83%.²²

The issue becomes more complicated when considering ID in the setting of coexisting conditions where serum ferritin may be elevated as an acute phase reactant. The most recent preoperative anemia guidelines from the British Committee on Standards in Hematology state that a serum ferritin of less than 30 mcg/L is a sensitive marker of iron deficiency; however, iron therapy may be indicated for non-anemic patients with low iron stores defined as ferritin less than 100 mcg/L and TSAT less than 20%, scheduled to undergo surgery.²³ Studies in the setting of congestive heart failure have defined ID as a ferritin less than 100 mcg/L or a ferritin less than 300 mcg/L AND a TSAT less than 20%.²⁴ In the setting of chemotherapy-induced anemia, the National Comprehensive Cancer Network Clinical Practice Guidelines in Oncology have defined absolute ID as ferritin less than 30 mcg/L AND TSAT less than 20%,

but functional iron deficiency in patients receiving erythropoiesis stimulating agents as a ferritin of 30-500 mcg/L AND TSAT less than 50%.²⁵

For the purposes of this study to ensure a population with a high likelihood of iron deficiency anemia, we have defined ID as a serum ferritin of less than 30 mcg/L.^{8,26,27}

2.1.4 Oral iron preclinical studies to date

This section is not applicable.

2.1.5 Oral iron clinical studies to date

The most common oral iron supplements currently used are ferrous gluconate, sulfate and fumarate each containing increasing doses of elemental iron (35, 60 and 100 mg elemental iron per 300mg tablet, respectively).⁸ Ferrous formulations have greater bioavailability than ferric preparations as it is in the ferrous form that iron is absorbed by the enterocyte. These supplements are inexpensive and often covered by provincial health plans. Although intravenous iron is also available, intravenous iron has been associated with rare serious infusion side effects including anaphylaxis, is hampered by a lack of resources for infusion facilities and nursing and thus, oral iron supplementation should be the first line of therapy when time permits.^{26,28,29}

Oral iron supplementation is associated with increasing hemoglobin in multiple studies in women, pregnant women and elderly patients.³⁰⁻³² However, the optimal dose and frequency of oral iron supplementation for treatment remains unclear. A recent systematic review of 21 studies in 10,258 women between menarche and menopause compared intermittent oral iron dosing (three times or less per week) compared with no intervention (or placebo) or daily oral iron dosing. When compared with intervention (or placebo), intermittent dosing reduced the risk of anemia (RR 0.73, 95% CI 0.56 to 0.95) and improved the concentration of hemoglobin (MD 4.58 g/L; 95% CI 2.56 to 6.59). When compared with daily supplementation, women on intermittent oral iron dosing presented more often with anemia (RR 1.26; 95% CI 1.04 to 1.51, six trials) although hemoglobin concentrations were similar (MD -0.15 g/L; 95% CI -2.20 to 1.91, eight trials). The review also found no difference in diarrhea, any side effects or adherence between intermittent and daily dosing, although very few trials reported on these outcomes.

Two more recent studies showed that dosing iron on alternate days may optimize iron absorption and may be preferable.^{33,34} The first study by Moretti et al sought to determine how the iron-induced increase in hepcidin influenced iron absorption for increasing doses of daily iron or twice-daily iron.³³ They found that doses of ferrous sulfate 60mg or higher resulted in an increase in hepcidin at 24 hours and resulted in a decrease of fractional iron absorption of 35-45%. Absolute iron absorption increased; however, with a six fold increase in dose, there was only a 3 fold increase in absorption. They also found that 3 doses given morning, afternoon then the following morning had the same total iron absorption as 2 morning doses. These findings suggested that alternate day dosing of oral iron at lower dosages (40-80mg) may maximize fractional iron absorption, increase dosage efficacy and improve tolerance of iron supplements.

Stoffel et al investigated two different dosing regimens in women aged 18 to 45 years with a serum ferritin less than 25 mcg/L who did not have anemia.³⁴ In the first study, they compared consecutive daily oral ferrous sulfate 60mg for 14 days (N=21) with alternate day dosing for 28 days (N=19). At the end of treatment, the fractional absorption was 16.3% vs. 21.8% (p=0.0013) and the total iron absorption was 131.0 mg vs. 175.3 mg (p=0.0010), favouring the alternate day dosing schedule. In the second study, they compared 120mg of elemental iron in the morning (N=10) with two split doses of 60mg given in the morning and evening for 3 consecutive days (N=10); then 14 days later, the groups

crossed-over. There was no difference in fractional absorption or total iron absorption between the two groups. The twice-daily divided dose had higher serum hepcidin concentrations. As a result, they concluded that oral iron supplements on alternate days, and as single doses might be a preferred dosing regimen and suggested confirming these findings in iron deficient anemic patients. The current proposed study attempts to address this gap in the literature.

2.1.6 Potential Risks

Side effects of oral iron supplementation include constipation, nausea, diarrhea, abdominal pain, vomiting, heartburn, flatulence and dark stools.^{8,35} When compared to placebo in randomized controlled trials, ferrous sulfate had an increased incidence of gastrointestinal (GI) side effects with an OR 2.32 (95% CI 1.74-3.08). The proportion of patients with GI side effects was 35% (range 10-90%) in the ferrous sulfate arms compared with 22 % (range 0-69%) in the placebo arms. The most common side effects were constipation, nausea and diarrhea with pooled estimates of incidence of 12%, 11% and 8% respectively.³⁵ Additional side effects included abdominal pain, vomiting, heartburn, flatulence and dark stools. There did not appear to be a significant association between dose and GI side effects. These side effects can have a significant impact on adherence with studies reporting up to 40% non-adherence and need to be carefully documented.³⁶ A recent study specifically developed a one page side effect questionnaire in patients on oral iron supplementation and was able to distinguish GI symptoms between participants on oral ferrous sulfate and placebo.³⁷ A modification of this questionnaire will be used in the current study.

2.1.7 Quality of Life Measures in IDA

Given the impacts of IDA extend beyond anemia and can affect an individual's physical, emotional and social well-being, quality of life measures are important to incorporate in the current study. The Functional Assessment of Chronic Illness Therapy (FACIT)-fatigue scale, previously the Functional Assessment of Cancer Therapy (FACT)-Fatigue scale, was developed and validated to assess cancer-related fatigue. More recently it has also been validated in other chronic conditions such as systemic lupus erythematosus, rheumatoid arthritis and chronic immune thrombocytopenia. To date, there has been one study that has examined the effects of IDA on fatigue severity and life measures, the results of which validated the use of the FACIT-fatigue scale.³⁸ The scale consists of 13 patient reported items as a measure of fatigue with a 7 day recall period. Items are scored from 0 (Not at all) to 4 (Very much so). Items are summed to a single fatigue score with a range of 0 to 52. Items can be reversed score to provide a scale in which higher scores represent better functioning or less fatigue. In this study, the internal consistency reliability was good (Cronbach's α = 0.93). Known group analysis using the FACIT-fatigue scale, using reverse scores, showed that there was a mean difference of 5.51 between the high hemoglobin group (hemoglobin > 120 g/L = mean 35.96 (SD 10.82)) and the low hemoglobin group (hemoglobin ≤ 90 g/L = mean 30.45 (SD 11.64)). The wide-spread use of the FACIT-fatigue scale and demonstrated appropriateness in IDA validates the choice of the FACIT-fatigue scale for use in the current study.

2.2 Current Proposal and Rationale

We propose a pilot, pragmatic, non-inferiority, open label randomized controlled trial (RCT) in outpatients with iron deficiency anemia to evaluate the effectiveness of oral ferrous sulfate 300mg (60mg elemental iron) once daily versus every other day to improve hemoglobin at 12 weeks post-initiation. The rationale for this study includes: (1) IDA is a common and prevalent condition with potential adverse consequences if left untreated; (2) optimizing effectiveness of oral iron supplementation while minimizing side effects will improve treatment for patients. We will enroll 52

patients in this pilot study at 2 centres. If this pilot trial is deemed to be feasible, we will plan a definitive multicentre trial.

2.3 Study Impact and Benefit

Because IDA is a global health problem, common in clinical practice and treatable, this study, although simple in its question and design, will have a significant practical impact on how clinicians treat outpatients with iron deficiency anemia and how patients tolerate therapy.

For the patient, the expected benefit from taking part in this study for the participant is the potential to improve and treat iron deficiency anemia. These potential changes may lead to improved symptoms associated with iron deficiency anemia, such as cognitive and physical functioning, and fatigue.

3.0 OBJECTIVES AND SCIENTIFIC AIMS

3.1 Primary Objective

The primary purpose of this trial is to determine the feasibility of performing a pilot pragmatic, open-label, randomized controlled trial to evaluate effectiveness of oral ferrous sulfate 300mg (60 mg elemental iron) once daily versus every other day to improve hemoglobin at 12 weeks post-initiation.

3.2 Trial Secondary Objective

The secondary purpose of this trial is to determine the effectiveness of alternative oral iron supplementation dosing regimens on iron deficiency anemia, including hemoglobin, while minimizing side effects to improve patient treatment.

3.3 Primary Outcome Measure

Feasibility: Time to enroll 52 patients

3.4 Secondary Outcome Measures

Feasibility

1. Proportion of eligible patients consenting to participate
2. Proportion of consenting patients receiving the allocated treatment
3. Proportion of treated patients completing 4 week and 12 week laboratory tests
4. Proportion of treated patients completing 4 week, 8 week and 12 week FACIT-fatigue scale
5. Proportion of treated patients completing 4 week, 8 week and 12 week side effect questionnaire
6. Proportion of treatment doses taken as per protocol (adherence)
7. Proportion of treated patients taking at least 90% of their prescribed doses
8. Proportion of treated patients requiring a step down in therapy due to adverse side effects

Clinical/Safety

9. Mean hemoglobin increment at 4 and 12 weeks
10. Proportion with complete hemoglobin response defined as hemoglobin greater than or equal to 120 g/L at 4 weeks and 12 weeks for women and greater than or equal to 130 g/L at 4 weeks and 12 weeks for men.

11. Change in reticulocyte count at 4 and 12 weeks
12. Change in ferritin, serum iron, TSAT at 12 weeks
13. Quality of life (FACT-fatigue scale) at 4, 8 and 12 weeks
14. Proportion with side effects and type of side effects at 4, 8 and 12 weeks
15. Proportion of patients who stop taking oral iron due to side effects at 4 and 12 weeks
16. Need for escalation in therapy (need for alternative oral iron therapy (including if a participant in the every other day group escalates to daily iron), need for intravenous iron, need for transfusion, visit to emergency department related to anemia) at 12 weeks
17. Proportion of patients with a drop in hemoglobin of 10 g/L or more from baseline at weeks 4 and 12

4.0 HYPOTHESES

We hypothesize that 52 patients will complete the trial within a 2-year period. This includes an expected drop out rate of 30% leaving 36 patients for analysis.

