5.0 STUDY METHODS

5.1 Study Design

This is a pilot pragmatic, non-inferiority, open label randomized controlled trial (RCT) in outpatients with iron deficiency anemia to evaluate the effectiveness of oral ferrous sulfate 300mg (60mg elemental iron) once daily versus every other day to improve hemoglobin at 12 weeks post-initiation. Patients will be randomized according to a computer-generated allocation sequence to receive either once daily dosing or every other day dosing. Randomization will be stratified by centre and baseline hemoglobin (hemoglobin \geq 100 g/L OR $<$ 100 g/L). Following randomization, patients will receive oral iron tablets for a period of 12 weeks, with clinical and subjective data collection occurring 1, 4, 8 and 12 weeks following the commencement of oral iron. The study will aim to recruit 52 patients in total, randomizing 26 patients to each study arm. This sample size includes an anticipated 30% drop out rate (see section 8.1).

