8.0 STATISTICAL CONSIDERATION

8.1 Sample Size and Sample Size Justification

The required sample size for this pilot RCT is calculated based on the primary outcome of the definitive study which is the mean hemoglobin increment in each group. For the every other day oral iron group to be considered non-inferior, the mean hemoglobin increment in the every other day oral iron group should not be more than 5 g/L less than the mean hemoglobin increment in the daily oral iron group. This is based on the Cochrane review³¹ of intermittent compared with daily dosing showing that the mean hemoglobin difference between intermittent and daily oral iron was -0.15 g/L (95% CI -2.2 g to 1.9 g). Looking at individual studies within the Cochrane review, the standard deviations for the baseline and end of intervention hemoglobin measurements were approximately 10 g/L. Stoffel et al³⁴ specifically studied the use of ferrous sulfate 300mg po daily over 14 days vs alternate day oral iron over 28 days. The baseline mean hemoglobin in each group was 128 g/L (-SD 117; + SD 140) and 132 g/L (-SD 125; +SD 140) respectively. At the end of the intervention, the hemoglobin was 132 g/L (-SD 125; +SD 140) and 136 g/L (-SD 129; +SD 144), respectively. Thus, the standard deviation for these 2 studies is closer to 10 g/L.

Table 2 below shows the sample size required to confirm non-inferiority of every other day oral iron compared with daily iron based on the true mean difference of the mean increment between the two groups, the standard deviation, the non-inferiority margin and the power of the study. The table also takes into account the adjusted sample size with a 30 % drop out considered.

Table 2: Sample size calculation

True difference of mean increment between two study groups, (g/L) ^{A, D}	Standard Deviation (SD) of the increment (g/L) ^B	Non-inferiority margin for the difference (g/L) ^C	Power	Total Sample size required to confirm non-inferiority	Adjusted sample size with 30% drop out considered ^E
0	5	>-5	80%	28	40
	7.5	>-5	80%	58	84
	10	>-5	80%	102	146

0	5	>-5	90%	36	52
	7.5	>-5	90%	80	116
	10	>-5	90%	140	200
-0.15	5	>-5	80%	28	40
	7.5	>-5	80%	62	90
	10	>-5	80%	108	156
-0.15	5	>-5	90%	38	56
	7.5	>-5	90%	84	120
	10	>-5	90%	148	212

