- A. Increment will be calculated from each subject first, and then mean increment for each study group. A difference in the mean increment will be calculated as mean increment in the every other day oral iron group minus mean increment in the daily oral iron group.
- B. Standard deviation (SD) was not available for the increment. It could be estimated from SDs of the pre- and post- treatment hemoglobin level and assumed correlation between pre- and post-hemoglobin. If SDs for the pre- and post- hemoglobin are equal to 10, and correlation between them is 0.5, the estimated SD for the increment is 10. If the correlation between pre- and post- is 0.75, then the estimated SD for the increment is 7.1.
- C. One sided 95% confidence interval of the difference between two groups in the hemoglobin increment will be calculated (every other day minus daily). If the bound of the confidence interval is greater than -5, then non-inferiority can be confirmed.
- D. If we assume the true difference between two groups is -0.15 as reported from the meta-analysis, the sample size required could be slightly larger.
- E. Total sample size was divided by 70% to account for a 30% drop out.

Given that this pilot trial is a proof-of concept study, a sample size of 52 patients was deemed appropriate. Therefore, we will aim to enroll 52 patients to determine the feasibility of the trial and to provide more accurate estimates of the numbers required for a definitive trial. The trial will be deemed feasible if we are able to enroll 52 patients over 2 years at two sites.

The trial will proceed until there are 52 enrolled patients and at least 36 patients who complete the trial to 13 weeks.

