8.2 Final Analysis Plan

The results of this pilot trial will be used to assess the feasibility and inform the design of the definitive trial. We will present point estimates of feasibility events, including enrolment, adherence to protocol and accrual, as proportions with 95% confidence intervals. We will present continuous data as means and standard deviations, or medians and inter-quartile ranges, as appropriate.

An intention-to-treat analysis will be performed on all patients randomized for the secondary efficacy outcome. A per protocol analysis will be conducted for patients who have taken at least 90% of the

prescribed doses. Subgroup analysis will be performed on the stratified groups with hemoglobin 100g/L or greater and hemoglobin less than 100g/L. Additional subgroup analyses will include: patients with ongoing bleeding (WHO grade 2 or higher) vs no bleeding; and normal vs. increased CRP (based on the normal range).

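### Intention-to-treat is promised for all randomized patients, but the only stated comparison drops anyone without week 12 hemoglobin, and that loss can be informative and differ by arm

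*Combined protocol and SAP*

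**What the plan says.** **Analysis set.** Section 8.2: "An intention-to-treat analysis will be performed on all patients randomized for the secondary efficacy outcome". It adds a per-protocol analysis (at least 90% of doses) and subgroups. It gives no model, covariates, missing-data rule or sensitivity analysis for hemoglobin.

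**Comparison.** Section 7.2, item 9, defines the increment as a patient's week 4 or week 12 hemoglobin minus baseline. The notes to Table 2 in section 8.1 give the only comparison. Note A averages individual increments by arm and takes every other day minus daily. Note C sets a one-sided 95% confidence interval for that difference against -5 g/L.

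**Numbers.** Section 5.1 plans on "randomizing 26 patients to each study arm". Section 4.0 says: "This includes an expected drop out rate of 30% leaving 36 patients for analysis". Section 8.1 continues the trial until 52 are enrolled with "at least 36 patients who complete the trial to 13 weeks".

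**Follow-up.**
- Section 5.3.4: patients who cannot take iron at all stay in follow-up if willing and if no withdrawal criterion is met.
- Sections 5.4.2.2 and 10.0: assessments end once therapy is escalated.
- Section 10.1: no further study data after withdrawal, although outcomes such as survival may be sought with permission.
- Section 10.2: withdrawn patients are asked to continue laboratory tests and quality-of-life assessments.

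**The concern.** A within-patient week 12 increment cannot be computed for a patient who has no week 12 hemoglobin. Unless another rule is given, such a patient leaves the week 12 comparison, whatever the analysis set is called.

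The loss need not be random. A patient whose hemoglobin has fallen by more than 10 g/L at week 4 is referred back to the responsible physician. If therapy is then escalated, study assessments stop. That removes poor responders from week 12 although their week 4 value is on file. One form of escalation, from every other day to daily, can occur only in the experimental arm, so both the amount and the meaning of the missing data can differ by arm.

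At stake are the secondary clinical estimates and the planning values they supply. Section 8.1 says the pilot should give more accurate estimates of the numbers needed for the definitive trial. A mean difference and SD taken from a selected subset would carry that selection forward.

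**Working it through.** **1. Reproduce the 36 and 52.** Inputs from Table 2: true difference 0, SD 5, margin 5 g/L, one-sided 5%, 90% power.

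n per arm = 2 × SD² × (1.645 + 1.282)² / 5² = 2 × 25 × 8.57 / 25 = 17.1, so 18 per arm and 36 in total.

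Note E: "Total sample size was divided by 70% to account for a 30% drop out". 36 / 0.70 = 51.4, taken to 52. In reverse, 52 × 0.70 = 36.4. Both figures reproduce. The sizing therefore allows for 52 - 36 = 16 patients (31%) with no usable increment.

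**2. Who has a week 12 increment under the written rules?**

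| Patient | Rule | Week 12 hemoglobin |
|---|---|---|
| Stops iron, stays in study | 5.3.4 | Expected |
| Escalates | 5.4.2.2, 10.0 | Not collected |
| Withdraws | 10.1 against 10.2 | Contradictory |

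Intravenous iron and transfusion count as escalation in 10.0 and as reasons for withdrawal in 10.1. For those patients the end of follow-up in 10.0 also conflicts with the continued testing in 10.2.

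**3. Bias of an observed-at-week-12 comparison.** Let m be the proportion missing in an arm, and g the amount by which the missing patients' mean increment falls below that of the observed patients. The observed mean exceeds the full mean by m × g, so

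bias (every other day minus daily) = m_E × g_E - m_D × g_D.

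The documents give neither m by arm nor g. All values below are assumptions; each scenario averages the plan's 30%.

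| Scenario | Calculation | Bias, g/L |
|---|---|---|
| 30% in each arm, equal gaps | 0.30g - 0.30g | 0 |
| 40% daily, 20% every other day, gap 5 to 10 in both | (0.20 - 0.40) × 5 to 10 | -1 to -2 |
| 30% in each arm, gap 5 to 10 in every other day only | 0.30 × 5 to 10 | +1.5 to +3 |
| 30% in each arm, gap 5 to 10 in daily only | -0.30 × 5 to 10 | -1.5 to -3 |

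Negative bias works against every-other-day dosing; positive bias favours a non-inferiority finding. Against the 5 g/L margin, 1 to 2 g/L is 20% to 40%, and 1.5 to 3 g/L is 30% to 60%.

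**4. Effect of the positive scenario on error.** With 18 per arm and SD 5, the standard error is 5 × √(2/18) = 1.67. At a true difference of -5, the chance of declaring non-inferiority is 1 - Φ(1.645 - bias/1.67):
- bias 0: 5%
- bias +1.5: about 23%
- bias +3: about 56%

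**5. Baseline adjustment, a separate matter from missing data.** With equal SDs before and after, as note B assumes, the variance of a change score is 2σ²(1 - ρ) and the baseline-adjusted variance is σ²(1 - ρ²). The ratio is (1 + ρ)/2: 0.75 at ρ = 0.5 and 0.875 at ρ = 0.75. These are the two correlations in note B. Adjustment thus cuts variance by 25% or 12.5% on the same patients.

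**The case against.** The strongest reply is that 36 comes from ordinary dropout inflation and that section 8.2 separately names intention-to-treat as the analysis set. A smaller evaluable number in the sizing does not prescribe a completers analysis, and the 36 completers in section 8.1 are a rule for continuing the trial. This stands. A reader might infer that the plan mandates completers-only analysis, but no section says so.

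Second, sections 5.3.4 and 10.2 mean that stopping iron is not the same as missing data, so intolerant patients may well supply a week 12 value. This also stands, but only in part: section 10.1 contradicts 10.2, and patients who escalate are still lost.

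Third, a reader might equate the 30% dropout (4.0, 8.1) with the roughly 30% expected not to tolerate iron (5.3.4) and conclude that the missing data are mainly due to intolerance. The documents never link the two figures. Section 2.1.6 also reports no significant association between dose and gastrointestinal effects, so a 40% against 20% split is only illustrative.

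Fourth, week 4 hemoglobin is scheduled for everyone, but patients are only reminded to have it done, and laboratory completion is itself a feasibility outcome. Near-complete week 4 data cannot be assumed. A model restricted to patients with a post-baseline value would still omit the earliest losses.

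Last, this is a feasibility pilot, and note C sits in the sizing for the definitive trial. That limits the importance of the gap but does not say how patients without week 12 data are to be analysed.

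**Conclusion.** The concern holds in a limited form. The plan promises intention-to-treat on all randomized patients but defines only a raw increment with an unadjusted interval, and it has no rule for patients without week 12 hemoglobin. Its follow-up rules end assessments at escalation and conflict on withdrawal. By default, the week 12 comparison risks resting on those observed at week 12, possibly selected differently by arm.

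Neither the size nor the direction of bias can be fixed from the documents. Under the assumptions shown it runs from zero, through -1 to -2 g/L, to +1.5 to +3 g/L. With 18 per arm and SD 5, the last range would raise the one-sided error from 5% to about 23% to 56%. A reader might infer that bias is certain or must favour one arm; the zero case and the opposite signs show that this does not follow.

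The consequence is confined to the secondary clinical estimates and the planning values for the definitive trial. Time to enroll 52 patients is unaffected.

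**What to change.** 1. In section 8.2, analyse hemoglobin at weeks 4 and 12 with a repeated-measures model including arm, visit, arm by visit, baseline hemoglobin, hemoglobin stratum and centre. Use every available post-baseline value, including week 4 values of patients who later escalate or withdraw. State that the model assumes the missing values are predictable from the observed ones.
2. Add a sensitivity analysis that includes all randomized patients, giving less favourable values to those lacking week 12 or any post-baseline hemoglobin. Vary the penalty separately by arm, for example over the 0 to 10 g/L span used above, because the sign of the bias depends on which arm is affected.
3. Reconcile sections 5.4.2.2, 10.0, 10.1 and 10.2, so that it is clear which patients should have hemoglobin measured after stopping iron, escalating or withdrawing. State how any value measured after escalation is treated in the analysis.
4. Reword section 4.0 to say that 36 patients are expected to have week 12 data. It now also says that 52 will complete the trial while expecting 30% to drop out.

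Items 1, 2 and 4 need only revised wording and modest extra analysis of data already scheduled. Item 3 is a drafting decision for the sponsor; whether it adds any measurements depends on how the conflict is settled.
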